## 7.2 PARTICIPANT DISCONTINUATION/WITHDRAWAL FROM THE STUDY

Subjects will be informed that they have the right to discontinue their participation at any time, and that their right to obtain appropriate treatment through normal referral channels will not be affected by their decision to participate or not participate. Subjects will also be informed that they have the right to demand that their responses not be included in the study, and that any publications resulting from the research will not identify them as individuals. The study doctor may decide to take a subject off this study if their condition gets worse, if they have serious side effects, or if the study team determines that it is no longer in the subject's best interest to continue. Other reasons for the study doctor to withdraw a subject from the study includes: if the subject is female and becomes pregnant, the subject needs treatment not allowed in the study (antidepressant, mood stabilizer and/or antipsychotic), the subject misses 4 talk therapy sessions in a row and has not maintained contact with their study therapist or any member of the study team. Though starting a benzodiazepine, sleep or ADHD medication is not encouraged in the study, if the situation arises during the study where it medically indicated by their own doctor that one of these type medications is needed, they will be allowed to start these medications and asked to notify the study team so it can be documented. The reason for participant discontinuation or withdrawal from the study will be recorded on the UNC REDCap tracking log form.

## 7.3 LOST TO FOLLOW-UP

A participant is considered lost to follow-up if he or she fails to return for four scheduled therapy visits in a row and is unable to be contacted by the study site staff.

The following actions are taken if a participant fails to return for a required study therapy visit:

- The site will attempt to contact the participant and reschedule the missed visit (must complete at least 1 therapy session before week 4 and at least 1 in weeks 5-8 and again at least 1 in weeks 9-12 and 13-15, if applicable). Study team will counsel the participant on the importance of maintaining the assigned visit schedule and ascertain if the participant wishes to and/or should continue in the study.
- Before a participant is deemed lost to follow-up, the investigator or designee will make every effort to regain contact with the participant (where possible, 3 telephone calls and emails, if necessary, these contact attempts should be documented in the participant's study file in REDCap).
- Should the participant continue to be unreachable, he or she will be considered to have withdrawn from the study with a primary reason of lost to follow-up.
- R33-If a participant is unable to return for the task visit due to sickness, weather, travel, etc but is attending the remote therapy sessions, the scheduled week 4, 8 and/or 12 task visit may be skipped, documented as a deviation but the participant is allowed to continue.

## 8 SAFETY

### 8.1 ADVERSE EVENTS AND SERIOUS ADVERSE EVENTS

### 8.1.1 DEFINITION OF ADVERSE EVENTS (AE)

Adverse event means any untoward medical occurrence associated with the use of an intervention in humans, whether or not considered intervention-related (21 CFR 312.32 (a)).

### 8.1.2 DEFINITION OF SERIOUS ADVERSE EVENTS (SAE)

An adverse event (AE) or suspected adverse reaction is considered "serious" if, in the view of either the investigator, DSMB, or sponsor, it results in any of the following outcomes: death, a life-threatening adverse event, inpatient hospitalization or prolongation of existing hospitalization, a persistent or significant incapacity or substantial disruption of the ability to conduct normal life functions, or a congenital anomaly/birth defect. Important medical events that may not result in death, be life-threatening, or require hospitalization may be considered serious when, based upon appropriate medical judgment, they may jeopardize the participant and may require medical or surgical intervention to prevent one of the outcomes listed in this definition.

### 8.1.3 CLASSIFICATION OF AN ADVERSE EVENT

#### 8.1.3.1 SEVERITY OF EVENT

*All AEs will be assessed by the study monitors (Drs. [name] and [name]) and monitored by the independent Data Safety Monitoring Board (DSMB), known as the BATA DSMB.*

For adverse events (AEs), the following guidelines will be used to describe severity.

- **Mild** – Events require minimal or no treatment and do not interfere with the participant's daily activities.
- **Moderate** – Events result in a low level of inconvenience or concern with the therapeutic measures. Moderate events may cause some interference with functioning.
- **Severe** – Events interrupt a participant's usual daily activity and may require systemic drug therapy or other treatment. Severe events are usually potentially life-threatening or incapacitating. Of note, the term "severe" does not necessarily equate to "serious".]

#### 8.1.3.2 RELATIONSHIP TO STUDY INTERVENTION

All adverse events (AEs) that occur during the study will be captured have their relationship to study intervention assessed by the study PIs who examine and evaluate the participant based on temporal relationship and his/her clinical judgment. The degree of certainty about causality will be graded using the categories below. In a clinical trial, the study product must always be suspect.

- **Definitely Related** – The AE is known to occur with the study intervention and the temporal relationship between the study intervention and event aligns. The event occurs in a plausible time relationship to study intervention administration and cannot be explained by concurrent disease or other drugs or chemicals.
- **Possibly Related** - there is a reasonable possibility that the study intervention caused the AE, or there is a temporal relationship between the study intervention and event. Reasonable possibility means that there is evidence to suggest a causal relationship between the study intervention and the AE. However, other factors may have contributed to the event (e.g., the participant's clinical condition, other concomitant events). Although an AE may rate only as

“possibly related” soon after discovery, it can be flagged as requiring more information and later be upgraded “definitely related”, as appropriate.

- **Not Related** – There is not a reasonable possibility that the administration of the study intervention caused the event, there is no temporal relationship between the study intervention and event onset, or an alternate etiology has been established.

#### 8.1.3.3 EXPECTEDNESS

*Expected adverse reactions are AEs that are known to occur for the study therapy and/or procedures being studied/used. Expectedness is assessed based on the awareness of AEs previously observed, not on the basis of what might be anticipated from the properties of the study intervention.*

*An AE or suspected adverse reaction is considered “unexpected” if it is not listed in the device labeling or is not listed at the specificity or severity that has been observed; or listed in the participant informed consent.*

*The Study PIs (UNC and Duke) will be responsible for determining whether an adverse event (AE) is expected or unexpected. An AE will be considered unexpected if the nature, severity, or frequency of the event is not consistent with the risk information previously described for the study intervention. The BATA DSMB will also be able to weigh in and recommend continuation, discontinuation, modification, or termination of a study based on emerging data (in the study and literature) and evaluation of risk/benefit ratio.*

#### 8.1.4 TIME PERIOD AND FREQUENCY FOR EVENT ASSESSMENT AND FOLLOW-UP

We will start collecting AEs/SAEs at the pre-treatment MRI visit at UNC’s BRIC and will continue to collect them through their final visit (i.e. most likely the post-treatment MRI visit at BRIC). All follow-up AEs/SAEs will end at their final study visit.

A trained study team member will ask about any changes in health and medications at each of the study visits as per the list of scheduled events table. In terms of the fMRI: After each participant is scanned, the PI, [name], will communicate with co-I [name], the UNC BRIC Director, to review any unanticipated problems (including but not limited to adverse events) to monitor subject safety. A weekly team meeting will be conducted to discuss research procedures.

*Quality assurance.* The Duke and UNC study teams will meet weekly to review any research issues that may have arisen during the past week as well as to monitor progress on subject recruitment and other research-related matters. Additional meetings are conducted on an as-needed basis.

Any Adverse Events will be reviewed by the study team at UNC and Duke as the events occur.

All AEs including not meeting the criteria for SAEs will be captured in their individual REDCap form. Information to be collected includes event description, time of onset, clinician’s assessment of severity, relationship to study (assessed only by those with the training and authority to make a diagnosis), and time of resolution/stabilization of the event. All AEs occurring while on study will be documented appropriately regardless of relationship.

Any medical condition that is present at the time that the participant is screened will be considered as baseline and not reported as an AE. However, if the study participant's condition deteriorates at any time during the study, the study team will discuss and it will be recorded as an AE.

In this study, if a subject experiences an SAE or study related, non-serious AE and they are not resolved at their final study visit, because it is a minimal risk study, it will not continue to be followed past the participant's final study visit.

---

#### 8.1.5 ADVERSE EVENT, SERIOUS ADVERSE EVENT REPORTING

*Reporting mechanisms of AEs & SAEs to the IRB.* In this study we will use the FDA's definition of adverse events (AEs) and serious adverse events (SAEs). It is not expected that any such AEs or SAEs will occur in this experiment. However, AEs and SAEs will be assessed by a trained study coordinator, study therapist or other approved study team member, and discussed at the weekly research staff meetings.

Any SAE during this collection period will be brought to the attention of the PI as soon as possible and not longer than 24 hrs. Any SAE (regardless of the study relatedness), will be reported to the Duke University Medical Center Institutional Review Board and/or UNC-Chapel Hill Institutional Review Board using the appropriate documentation within 5 days of the event. Unexpected study related SAEs will be reported to the overall sponsor, NIMH within 10 business days. This will be the responsibility of the 2 PIs, Drs. [name] & [name]. The Duke University Medical Center IRB/UNC-Chapel Hill IRB will decide as to whether additional reporting requirements are needed.

Reporting of non-study related, non-serious AEs are not reported to the IRB, overall sponsor, and not entered on the study AE tracking log, however they will be entered on the subject's individual adverse event pages within REDCap and checked at every study visit (both at UNC & Duke).

Non-serious AEs that are deemed study related will be reported to the IRB and overall sponsor with annual reporting and entered on the subject's individual adverse event page in REDCap. These will be reported to the DSMB as per the DSMB scheduled reporting.

---

#### 8.1.6 REPORTING EVENTS TO PARTICIPANTS

Participants will be told about new information that may affect their health, welfare, or willingness to stay in the study. The study PIs may decide to take someone off this study if their condition gets worse, if they have serious side effects, or if the study team determines that it is no longer in the participant's best interest to continue. The Duke PI (supervisor of the study therapists) meets weekly with the study therapists and if there appears to be significant worsening with no clear signs of current study potential benefits, the study therapist will then meet with the participant at the next therapy session (or sooner, if necessary) and discuss having the participant stop and be provided resources to follow-up with such as medications, therapy and other interventions outside of the study.

If the BATA DSMB suggested any changes to the risk/benefit ratio to the study, these updates are given to participants in the form of a new consent and asked to review and sign and date that they are been given the new information and still will continue to participate (or can refuse to continue).

---

#### 8.1.7 REPORTING OF PREGNANCY

*Pregnancy is not an adverse event, but study participants who do become pregnant while enrolled in the study are asked to report this to their study therapist or a study team member immediately. They will be dropped from the study since it is not recommended they undergo a follow-up 7T MRI and if applicable, a follow-up PET scan using the radioactive tracer.*

## 9 STATISTICAL CONSIDERATIONS

### 9.1 SAMPLE SIZE DETERMINATION

**Aims 1, 2, and 5:** To evaluate whether BATA produces changes in neural responses to reward anticipation and reward outcomes that (1) exceed our *a priori* target engagement criteria; (2) exceed changes due to a comparison treatment; and (3) does not impact neural responses to threat. To evaluate relations between BATA dose and neural target engagement by examining changes in reward responding with fMRI scans 8, 12 and 16 weeks after starting the 15-week treatment.

Power is calculated for Aim 1 fMRI analyses because of its smaller sample, and the Aims that involve all 210 participants will have higher power because of the larger sample and optimized BATA dose. For Aim 1 we will enroll 30 outpatients per group to have complete data from 25 per group. Based on our pilot data demonstrating increased right CN activation during reward anticipation and decreased rACC activation during reward outcomes, we calculated an effect size of approximately  $z=4.1$ . Conservatively, we estimate the effect size for the increased right CN activation and reduced rACC activation will be in the range of  $z = (0.75-1.25)$ . Our models will thus have  $>90\%$  power at  $\alpha=0.025$ .

**Aims 3 and 4:** To evaluate the effects of BATA versus MBCT on anhedonic symptoms, functional outcomes, and behavioral indices of reward sensitivity. Our power analysis addresses the effects of BATA versus MBCT on SHAPS scores (conducted with Gpower) as an ANCOVA with two groups and two timepoints. With 65 subjects per treatment group with complete data at post-treatment,  $\alpha = .05$ , and assumed correlation between assessments of 0.35 (based on preliminary studies), we will have 98% power to detect small ( $f = .2$ ) effects. Pilot data in depressed patients indicated a large effect from pre-to post-treatment ( $d=1.24$ ,  $f = .62$ ), and we are powered to detect these effects. We are 80% powered to detect the interactions with effects as small as  $f = .14$ .

**PET Power Analyses:** Sample sizes are dictated by the limitations of this funding mechanism, and we note that the majority of published molecular imaging studies have had relatively modest sample sizes. We also note that one advantage of our approach is that both phasic and tonic DA states are acquired during the same scan, thereby allowing for statistical models that use within-subjects variance calculations. Finally, we highlight that the test-retest stability of [11C]raclopride-derived DA binding potentials is very good (ICC = .82 for the NAcc [46]). Our power analysis is based on power to detect group differences in the intra-subject correlation between DA release and change in BOLD signal. Assuming a standard deviation in DA-mediated binding potential changes of 0.3 (approximately 10%), we will be powered to detect a  $>15\%$  change in DA binding (?BP%) with a power of 0.85 and a false discovery rate of 2.5%. This sample size is limited by the funds available through this grant mechanism and the extremely high cost of PET imaging.

*EMA Power Analysis.* Given our sample size, we consider EMA to be preliminary data that may be used to estimate effect sizes for future grant applications that use EMA as an outcome measure for anhedonia clinical trials. Additionally, the proposed structural equation models are very complicated and may need to be adjusted. With the sample size of the R61 phase of the parent grant, the proposed analyses should have medium power (50% or more) to identify paths if the paths correspond to partial correlations of  $|0.10|$  or larger. By continuing to collect EMA data in R33, we hope to increase our sample size and also explore changes after wk 4, 8, and 12 (if applicable) computer tasks, thus EMA is not only linked to pre- and post treatment MRI scan visits.

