**Aims 3, 4, and 5 pertain to all 210 participants randomized (n=105 to receive BATA and n=105 to receive MBCT).**

**Aim 3:** To evaluate the effects of BATA versus an active comparison treatment on anhedonic symptoms and functional outcomes.

**Aim 4:** To evaluate the effects of BATA versus an active comparison treatment on behavioral indices of reward sensitivity.

**Aim 5:** To evaluate the effects of BATA versus a comparison treatment on neural response to rewards.

PET Aims specifically refer to the 30 subjects who consent to the optional PET sub-study:

**Aim 1 (PET):** To evaluate the effects of BATA, relative to a comparison treatment, on PET-derived measures of DA functioning during incentive processing. We hypothesize that BATA, but not the comparison treatment, will result in increased phasic striatal DA release but will not influence background DA striatal tone.

**Aim 2 (PET):** To evaluate relations between treatment-related changes in fMRI-derived mesocorticolimbic activation and PET-derived DA functioning in the BATA-treated group. We hypothesize that normalization of fMRI-derived mesocorticolimbic activation due to BATA specifically will be associated with increased phasic DA release but no change in background DA tone during incentive processing.

Exploratory Aims include the data from the EMA optional study: Passive location tracking (PLT) data during the period of EMA monitoring will be collected via the MetricWire app to allow us to compare distance traveled before and after both treatments as a secondary, exploratory measure of behavioral activation. Follow-up analyses will evaluate relations between motion tracking, behavioral, brain, and clinical measures of response to both treatments.

**Specific Aim 3 (EMA):** To evaluate if BATA, relative to a comparison treatment, produces improvements in real-world positive affect and the use of BATA skills. We hypothesize that BATA, but not the comparison treatment, will be associated with improvements in real-world positive affect and the use of BATA skills.

**Specific Aim 4 (EMA):** To evaluate relations between treatment-related changes in fMRI-derived mesocorticolimbic activation and real-world positive affect and the use of relevant BATA skills in the

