**Aims 3, 4, and 5 pertain to all 210 participants randomized (n=105 to receive BATA and n=105 to receive MBCT).**

Aim 3: We predict that BATA will produce clinically and statistically significant improvements in anhedonia and functional outcomes that exceed those due to the comparison treatment.

Aim 4: We predict that BATA will improve behavioral indices of reward sensitivity.

Aim 5: To evaluate the effects of BATA versus a comparison treatment on neural response to rewards. We predict that, consistent with Aim 1, BATA will increase right CN activation during reward anticipation and decrease rACC activation during reward outcomes and that BATA will not decrease amygdala activation to threat, confirming the specificity of BATA for targeting these positive valence neural systems. This Aim will provide a replication and extension of Aim 1 findings with a larger sample and with an optimal treatment dose.

In the PET sub-study, Hypothesis 1- BATA, but not the comparison treatment, will result in increased phasic striatal DA release but will not influence background DA striatal tone. Hypothesis 2- that normalization of fMRI-derived mesocorticolimbic activation due to BATA specifically will be associated with increased phasic DA release but no change in background DA tone during incentive processing.

This is not a pilot study but rather a Phase I/II study. The R61 phase (Phase I) of the protocol is designed to provide preliminary data for the acceptability, identification of the optimal dose of BATA as well as the preliminary efficacy of BATA in subjects with anhedonia compared to those in the MBCT control group. Using the fMRI data, this phase of the study will test if BATA produces changes in neural responses to reward anticipation and reward outcomes that exceed changes in the MBCT group and does not impact neural responses to threat. As such, a small group (N = 60) of subjects will be in this blinded phase and they will complete up to a total of 4 fMRI scans (pre-treatment, week 8, 12 and post-treatment). The R61 study will be entering a no-cost extension at the end of the current project period to allow for completion of data collection for this phase. Due to limited funds, the number of scans obtained is being reduced from up to 4 scans to two scans (pre- and post-treatment.) for participants

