### **Study Visits:**

Potential participants will complete the following:

- 1) A phone or online screen to determine initial eligibility via UNC's REDCap

- 2) A 1-2 clinical characterization visit(s) to determine eligible, and, if eligible, to characterize participants clinically. During COVID, can be split remote/in-person.
- 3) A pre-treatment 7 Tesla (7T) fMRI scan & if one of the first 60 subjects enrolled, have an initial blood draw of 10ml (2tsp). Update, the NARSAD blood protocol had entered an extension and has additional funds so up to 210 participants, in both phases, will have an initial blood draw of 10ml (2tsp). **As of 6/26/20, the blood protocol will no longer continue for any new participant enrolled in the study. As of the NCE 2022, this current amendment, imaging of new participants will end. Only enrollment into the therapy portion at Duke will continue.**
- 4) Patients will then be assigned randomly to the experimental treatment (BATA) or comparison treatment (Mindfulness Based Cognitive Therapy (MBCT)) for approximately 15 weeks of treatment.
- 5) The first 60 patients enrolled (n=30 who receive BATA and n=30 who receive MBCT) will additionally complete two additional, mid-treatment, fMRI scans as well as an additional blood draw at all other MRI visits. The 1st phase of the study entered the R61 no cost extension at the end of the project period & due to limited funds, participants will no longer be receiving up to 4 scans. Participants who consent at UNC on or after 11/1/18 will receive only pre- and post-treatment scans (2 scans total). **The R61 no cost extension has ended and the study has entered the larger R33 phase of the study and participants will continue to receive only pre and post treatment scans (2 total) and no bloodwork will be collected starting summer 2020 for new participants. \*\*No new enrollment to imaging at UNC will occur with the approval of the June 2022 NCE amendment.**
- 6) A post-treatment clinical characterization visit
- 7) A post-treatment 7T scan

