Therapy sessions are provided at no cost to the participant and they will be given a parking pass, if applicable. At weeks 4, 8, & 12 of therapy, they will complete the computer effort/reward tasks & will receive between \$12-19 (\$10 + \$2-9 based on task performance) at each of those 3 visits for a total of \$36-57 at these 3 therapy visits in addition to parking or bus pass. **Again, during COVID-19, if tasks cannot be conducted at an in-person visit, the participant would still be paid the minimum of \$12 for these visits, if applicable.**

UNC: For completing each MRI brain scan visit, subjects will receive \$75 up to as much as \$110 depending on their responses to the scanner task plus a parking or bus pass, if applicable. Thus total fMRI compensation for the study will be between \$150-440. **Participants enrolled at UNC as of 11/1/18, will only have a pre & post treatment MRI scan and thus total fMRI compensation for the study will be between \$150-220.**

Based on our previous experience, retention for psychotherapy trials from pre- to post-neuroimaging sessions is approximately 81%.

**EMA Optional Sub-study:** Participants will be compensated \$10 per week of EMA participation, and will receive a bonus of \$1 per survey completion if they complete more than 8 responses in a given week. Thus, participants will have the potential to earn up to \$52 over the course of the four weeks of EMA. In the 1st phase of the study- a R61 no cost extension & due to limited funds-participants who enrolled in the 1st phase on or after 11/1/18, have been completing EMA after pre and post MRI scans & thus can earn up \$26 over the course 2 weeks of EMA instead of \$52.

**R33 EMA compensation:** **With the additional wks 4, 8, and 12 (if applicable) adding to the pre and post treatment scan timepoints, participants who agree to the optional EMA portion of the study, will have the potential to earn up to \$65 over the course of 5 weeks of EMA instead of only \$26 from the R61 no cost extension.**

**PET sub-study:** Subjects will be compensated a range of \$160 - \$200 per scan, to be determined by the computer activity that they complete while in the scanner. If they are unable to complete the PET imaging with computer activity after getting in the scanner, they will be paid \$20/hour for that session.

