## 6 STUDY INTERVENTION

### 6.1 STUDY INTERVENTION(S) ADMINISTRATION

#### 6.1.1 STUDY INTERVENTION DESCRIPTION

##### **Behavioral Activation Treatment for Anhedonia (BATA)**

Treatment in the R61 phase (Phase I) will consist of up to 15 weekly 45-minute sessions. This duration maybe modified in the R33 phase as a result of R61 phase Aim 2 analyses. Update for R33: Duration will remain as 8-15 weeks of treatment. Session 1 provides orientation and psychoeducation on anhedonia, and activity monitoring is introduced. Sessions 2-3 include structured values assessments of 10 life areas (e.g., Family Relationships, Employment/Career) to enhance motivation for sustained behavior change and to clarify goals. Following goals clarification, an activity hierarchy is developed, establishing a set of idiographic behavioral targets across life areas prioritized by ease of implementation to scaffold task engagement during the course of treatment. Session 4 focuses on reduction of avoidance. Sessions 5 and above assess completion of goals from the previous sessions, troubleshoot barriers to goal completion, and assign goals for the coming weeks. In the R33 phase, the minimum number of sessions will be 8 to allow for all planned content to be introduced, with a maximum of 15 sessions. Inherent in this structure is therapist assistance in setting achievable goals, which is often impaired in the context of anhedonia. Embedded in the review of goal completion is heightened awareness of anhedonia and identification of behaviors that are associated with greater positive response in the form of subjective importance and enjoyment. Those behaviors then form the basis of goals for the following weeks. The therapist uses motivational techniques to elicit goal-directed behaviors outside session including tying goals to the patient's identified values, open-ended questioning and reflective listening, and functional analysis to select behaviors maximally likely to achieve the patient's goals. Increased positive affect and decreased negative affect are theorized to result from increased contact with potential reinforcers through reduced behavioral avoidance. Maladaptive behaviors such as avoidance decrease the effectiveness of positive events in shaping future behavior, weakening the learned association between adaptive behaviors and positive outcomes. In this way, the overarching goal of BATA is to encourage the

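### Aim 5 (7T fMRI) is still sized at all 210 participants although imaging of new participants ended with the June 2022 amendment, and the optimized dose cited for its power is undocumented

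*Combined protocol and SAP*

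**What the plan says.** **Size of Aim 5.** Section 3 states that "Aims 3, 4, and 5 pertain to all 210 participants randomized (n=105 to receive BATA and n=105 to receive MBCT"; Section 4.1 repeats this. Aim 5 is the neural response to rewards, analysed in Section 9.2 by comparing fMRI activation before and after treatment. The synopsis (Section 1.1) lists activation in the Monetary Incentive Delay task among the primary endpoints.

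**Power.** Section 9.1 calculates fMRI power for Aim 1 only: "For Aim 1 we will enroll 30 outpatients per group to have complete data from 25 per group". It continues that "we estimate the effect size for the increased right CN activation and reduced rACC activation will be in the range of" 0.75 to 1.25, and claims more than 90% power at alpha 0.025. Aim 5 is covered by one comparative statement: "the Aims that involve all 210 participants will have higher power because of the larger sample and optimized BATA dose". Section 4.1 adds about Aim 5: "This Aim will provide a replication and extension of Aim 1 findings with a larger sample and with an optimal treatment dose".

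**Imaging stop.** Section 4.1, Study Visits, says that "No new enrollment to imaging at UNC will occur with the approval of the June 2022 NCE amendment", and that only enrolment into therapy at Duke continues. Section 5.2 drops the MRI exclusion for therapy participants because imaging is being removed for lack of funds.

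**Dose.** Section 6.1.1 first allows the R33 duration to be changed after the Aim 2 analyses, then says: "Update for R33: Duration will remain as 8-15 weeks of treatment".

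**The concern.** Aim 5 needs a pre-treatment and a post-treatment scan. A participant who joined after the imaging stop has neither and cannot enter the Aim 5 analysis. The size stated for Aim 5 is therefore one that the current design does not deliver, and the only statement about its power points to that size.

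The second reason offered for higher power, an optimized dose, has no support elsewhere in the document. No Aim 2 result or selected dose is reported, and the R33 duration is described as unchanged.

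At stake is how Aim 5 is read. If the figures stay as they are, a reader could take a null result as coming from 105 per arm, when the imaged sample is smaller by an unknown number.

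**Working it through.** **1. Inputs**

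- Aim 1: 30 enrolled and 25 complete per group; effect 0.75 to 1.25; alpha 0.025; power above 90% (Section 9.1).
- Aim 5: 210 participants, 105 per arm (Sections 3 and 4.1).
- Retention: Section 5.4 says "retention for psychotherapy trials from pre- to post-neuroimaging sessions is approximately 81" per cent.
- Number scanned before the June 2022 stop: not given. Values of 100, 150 and 210 are assumptions used to show a range.
- Further assumptions: the effect size, labelled z in the plan without definition, is read as a standardized mean difference; alpha is two-sided (the plan does not say); arms are equal; the planned ANCOVA is simplified to a two-sample comparison of change.

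**2. The plan's own figure (Aim 1)**

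For a within-group change with n = 25 and d = 0.75, the noncentrality is 0.75 × √25 = 3.75. Power at two-sided alpha 0.025 is 90.5% (noncentral t, 24 df), so the claim of more than 90% reproduces in that form. For the BATA versus MBCT contrast with 25 per arm, the noncentrality is 0.75 × √(25/2) = 2.65 and power is 63%. At d = 1.0 it is about 88%, and at 1.25 about 98%. The between-group contrast is the one used below, because Aim 5 compares treatments.

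**3. Aim 5 over a range of scanned totals**

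Completers per arm: n = scanned × 0.81 / 2, rounded down.

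- 210 × 0.81 / 2 = 85.05, so 85
- 150 × 0.81 / 2 = 60.75, so 60
- 100 × 0.81 / 2 = 40.5, so 40

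Power = P(T > t(0.9875, 2n − 2)), where T is noncentral t with 2n − 2 df and noncentrality d√(n/2). Solving for d at 90% power gives the detectable difference. The normal approximation d ≈ (2.241 + 1.282) × √(2/n) gives 0.79 at n = 40, against 0.80 from the t calculation.

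| Case | Completers per arm | Detectable difference, 90% power | Power at 0.75 SD | Power at 0.5 SD |
|---|---|---|---|---|
| 210 scanned (as the plan states) | 85 | 0.54 SD | above 99% | 84% |
| 150 scanned (assumed) | 60 | 0.65 SD | 97% | 68% |
| 100 scanned (assumed) | 40 | 0.80 SD | 86% | 48% |
| Aim 1, plan's own completers | 25 | 1.02 SD | 63% | 30% |

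**4. Dose: the statements side by side**

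- Sections 4.1 and 9.1: Aim 5 uses an optimal or optimized dose.
- Section 6.1.1: Aim 2 may lead to a modified duration; the R33 update keeps 8-15 weeks.
- Section 4.1, Study Visits: the mid-treatment scans that feed Aim 2 stopped for participants consenting at UNC on or after 11/1/18.
- No section reports an Aim 2 estimate or a dose chosen from it.

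The dose argument therefore cannot be checked or turned into a power gain.

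**The case against.** The strongest defence is that the sentence in Section 9.1 is comparative. It claims more power than Aim 1, not a specific power with 210. R33 participants had pre- and post-treatment scans before June 2022, and Aim 5 pools them with the R61 scans. Even with 100 scanned, the detectable difference is 0.80 SD against 1.02 SD for Aim 1. This stands: a reader might infer that the larger-sample argument collapses, but the documents do not support that.

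The sentence also covers Aims 3 and 4. The imaging stop does not remove participants from those aims, because therapy enrolment continues, so 210 can remain there. This also stands.

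A reader might further infer that dose optimization never took place. That goes too far. Keeping 8-15 weeks could itself be what Aim 2 led to; the text does not say either way. What can be said is that an optimized dose is not documented.

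Finally, the scanned total is unknown, and values nearer 210 would make the loss small: at 180 scanned (180 × 0.81 / 2 = 72.9, so 72 per arm) the detectable difference is 0.59 SD. That is fair, and it is why the table is only an illustration. The imaging stop is also openly stated, and the synopsis words the R33 total as up to 210. Neither point repairs Sections 3, 4.1 and 9.1, which still assign Aim 5 to all 210 randomized participants.

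**Conclusion.** The point holds as an internal inconsistency, not as a miscalculation. The Aim 5 size of 210 (105 per arm) conflicts with the imaging stop, and Aim 5 has no power figure that survives its removal. The Aim 5 sample falls short of 210 by the number enrolled after the amendment. The documents do not give that number, but they say that such enrolment was to continue.

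Higher power than Aim 1 probably survives, provided the imaged total is meaningfully above 60. Over the assumed range of 100 to 150 scanned, the difference detectable with 90% power is 0.80 to 0.65 SD, rather than 0.54 SD with 210. At the low end of the plan's own effect range (0.75) power stays at 86% to 97%; at 0.5 SD it falls to 48% to 68%. These figures depend on the assumed counts, 81% retention, two-sided alpha 0.025 and the reading of the effect size as a standardized difference. No power gain can be credited to the dose on the present text.

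**What to change.** - In Sections 1.1, 3, 4.1 and 9.1, define the Aim 5 population as participants enrolled in imaging before the June 2022 amendment.
- For Aim 5, replace 210 and 105 per arm by the actual number scanned and the number with both pre- and post-treatment scans, by arm.
- State the detectable difference for those counts at the plan's alpha of 0.025, giving the sidedness and the effect-size metric.
- Reconcile the optimal or optimized dose in Sections 4.1 and 9.1 with the unchanged duration in Section 6.1.1. Remove it as a reason for higher power unless an Aim 2 result is cited in support.
- Keep 210 for Aims 3 and 4.

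The cost is a wording change plus a count from the imaging log. The stated size and precision of Aim 5 become less favourable.
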